2 LIST OF ABBREVIATIONS

Term	Definition / description
ABCB1	ATP-binding cassette sub-family B member 1 (gene encoding for P-gp)
ADCS-ADL	Alzheimer's Disease Cooperative Study/Activities of Daily
ADCS-MCI-ADL	ADCS-ADL for mild cognitive impairment
AChE-Is	Acetylcholine Esterase Inhibitors
AD	Alzheimer's Disease
ADAS-cog	Alzheimer's Disease Assessment Scale-cognitive subscale
AE	Adverse Event
AESI	Adverse Event of Special Interest
AUC	Area under the Curve
BCRP	Breast cancer resistance protein
b.i.d	bis in die (twice a day)
BPM	Beats per Minute
CDR-SB	Clinical Dementia Rating Scale–Sum of Boxes
BRPM	Blinded report planning meeting
CI	Confidence Interval
CRF	Case Report Form
CT	Concomitant therapy
CCT	Cranial Computer Tomography
CSF	Cerebrospinal fluid
C-SSRS	Columbia Suicide Severity Rating Scale
CTC	Common Terminology Criteria
CTMF	Clinical Trial Master File
CTP	Clinical Trial Protocol
CTR	Clinical Trial Report
CYP	Cytochrome
DAT	Dementia of Alzheimer Type
DMC	Data Monitoring Committee
DMG	Dictionary Maintenance Group
DNA	Deoxyribonucleic Acid
DM&SM	Boehringer Ingelheim Data Management and Statistics Manual
DRA	Drug Regulatory Affairs
eCRF	Electronic Case Report Form
EDC	Electronic Data Capture
EM	Extensive metabolizer
EMEA	European Agency for the Evaluation of Medicinal Products
EudraCT	European Clinical Trials Database
FAS	Full Analysis Set
FTA	Fluorescent treponemal antibody absorbent test
GCP	Good Clinical Practice

Proprietary confidential information © 2017 Boehringer Ingelheim International GmbH or one or more of its affiliated companies

HR	Heart Rate
IB	Investigator's Brochure
ICF	Informed consent form
ICH	International Conference on Harmonisation
IEC	Independent Ethics Committee
IM	Intermediate metabolizer
IPV	Important protocol violation
IRB	Institutional Review Board
ISF	Investigator Site File
IRT	Interactive Response Technology
MCPMod	Multiple Comparisons & Modelling
MedDRA	Medical Dictionary for Drug Regulatory Activities
MI	Multiple Imputation
MMRM	Mixed model repeated measures
MMSE	Mini-Mental-State-Examination
MQRM	Medical Quality Review Meeting
MRI	Magnetic Resonance Imaging
MST	Medical Subteam
NMDA-R	N-methyl-D-aspartate receptor
NTB	Neuropsychological Test Battery
P-gp	P-glycoprotein
O*C	Oracle Clinical
OC	Observed cases
OR	Original result
PD	Pharmacodynamics
PM	Poor metabolizer
POC	Proof of Concept
PPS	Per protocol set
PSTAT	Project Statistician
PK	Pharmacokinetic
PM	Poor metabolizers
PV	Protocol violation
Q1	Lower quartile
Q3	Upper quartile
RDC	Remote Data Capture
REP	Residual Effect Period
RPR	Rapid Plasma Reagin
q.d.	quaque die (once a day)
SAE	Serious Adverse Event
SD	Standard Deviation
SE	Standard Error
SMQ	Standardised MedDRA query
SOC	System organ class

Proprietary confidential information © 2017 Boehringer Ingelheim International GmbH or one or more of its affiliated companies

SPC	Summary of Product Characteristics
TCM	Trial Clinical Monitor
TDMAP	Trial Data Management and Analysis
[REDACTED]	[REDACTED]
TESS	Treatment emergent signs and symptoms
TMM	Team Member Medicine
TMW	Trial Medical Writer
TOC	Table of contents
TS	Treated Set
TSAP	Trial Statistical Analysis Plan
UM	Ultrarapid metabolizer

3 INTRODUCTION

As per ICH E9, the purpose of this document is to provide a more technical and detailed elaboration of the principal features of the analysis described in the protocol, and to include detailed procedures for executing the statistical analysis of the primary and secondary variables and other data.

This TSAP assumes familiarity with the Clinical Trial Protocol (CTP), including Protocol Amendments. In particular, the TSAP is based on the planned analysis specification as written in CTP Section 7 “Statistical Methods and Determination of Sample Size”. Therefore, TSAP readers may consult the CTP for more background information on the study, e.g., on study objectives, study design and population, treatments, definition of measurements and variables, planning of sample size, randomization.

SAS Version 9.4 will be used for all analyses.

4 CHANGE IN THE PLANNED ANALYSIS OF THE STUDY

The following changes were made:

The data for patients entered prior to Amendment 3 will be handled as follows:

- The data for assessments removed from the study completely or for a specific visit due to the amendment will be summarized descriptively.

5 ENDPOINT

Efficacy, safety and tolerability of different doses of BI 409306 compared to placebo in patients with prodromal AD are the objectives of this trial.

5.1 PRIMARY ENDPOINT

The primary endpoint is:

The Neuropsychological Test Battery (NTB) response, defined as change from baseline in total z-score after 12 weeks of treatment.

For each patient's raw scores on each of the 9 NTB tests will be converted to the standardized z-score using the baseline means and standard deviations (SDs) for each test. The baseline means and SDs will be calculated using all randomized patients. The resultant z-scores will be averaged to obtain a total z-score, incorporating all 9 NTB tests. Change from baseline will be calculated as the post-baseline composite z-score minus the pre-treatment z-score, such that a positive change indicates an improvement from baseline. The measurements taken at Visit 3 will be considered as baseline values. Further information can be found in [section 9.1](#).

5.2 SECONDARY ENDPOINTS

5.2.1 Key secondary endpoint

This section is not applicable as no key secondary endpoint has been specified in the protocol.

[figure not shown]
5.2.2 Other Secondary endpoints

Secondary efficacy endpoints are the same as detailed in Section 5.1.1 of the protocol. Namely, they are the following:

[figure not shown]
[figure not shown]
Change from baseline in the ADCS-MCI-ADL (Alzheimer's Disease Cooperative Study/Activities of Daily Living for mild cognitive impairment) score after 12 weeks of treatment.

Change from baseline CDR-SB (Clinical Dementia Rating – Sum of Boxes) after 12 weeks of treatment

Change from baseline in ADAS-Cog11 (Alzheimer's Disease Assessment Scale cognitive subscale) total score after 12 weeks of treatment.

Proprietary confidential information © 2017 Boehringer Ingelheim International GmbH or one or more of its affiliated companies

6 GENERAL ANALYSIS DEFINITIONS

6.1 TREATMENTS

For regimen details refer to Section 3.1 of the CTP.

The treatments and treatment periods are defined as follows:

Table 6.1: 1 Treatment descriptions

TPATT	Long Name	Short Name
A	BI 409306 10 mg QD	10mg QD
B	BI 409306 25 mg QD	25mg QD
C	BI 409306 50 mg QD	50mg QD
D	BI 409306 25 mg BID	25mg BID
E	Placebo	Placebo

Table 6.1: 2 Definition of analyzing treatment period

Label	Interval	Start Date	Start time
Screening	Screening	Date of informed consent	00:00
Placebo Run-in (PBORI)	Run-in	Date of first administration of run-in medication	Time of first administration of run-in medication 12:00 if missing
BI 409306 10mg QD BI 409306 25mg QD BI 409306 50mg QD BI 409306 25mg BID Placebo	Treatment	Date of first administration of study medication	Time of first administration of study medication 12:00 if missing
Post-treatment	Post-treatment	Date of last intake of study drug + X+1 (see definition of X below)	00:00
Post-study	Post-study	Start date = Last contact date, defined as the maximum of (Trial completion date, last study drug intake + X) +1	00:00

Proprietary confidential information © 2017 Boehringer Ingelheim International GmbH or one or more of its affiliated companies

For safety analyses, data up to 7 days after last treatment intake will be considered as on treatment for AEs and for laboratory values. To clarify;

- Screening: starts from the date of informed consent to the date of first administration of run-in medication.
- Placebo run in period: starts from the date of first administration of run-in medication to the date of first administration of randomized study drug.
- On treatment: From the first intake of randomized study drug to last intake of randomized study drug + X days, where X=7 days for safety laboratory and AE.
- Post-treatment: From end of on-treatment period until last contact. Last contact date is defined in Table 6.1: 1. Post treatment period is not applicable for patients with last contact equal to 'last intake + X + 1 days' where X is 7 days as previously specified.
- Post study: From day after last contact defined in [Table 6.1: 1](#). If period starts at end of on-treatment period then post-treatment period is not applicable.

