### Clinical safety

In healthy volunteer trials [[U12-1034-01](#), [U13-1182-01](#), [U12-2165-01](#), [U13-1303-01](#), [c02098989-02](#)], the most frequent drug related adverse events were visual side effects (such as sensation of flashing lights, altered color perception, photophobia / increased sensitivity to light or blurred vision) that occurred shortly after dosing and mostly resolved within 1 h, i.e., in close connection to maximum BI 409306 plasma concentrations as the concentration-time profile sharply and steeply peaks within the first 1-2 hours and then rapidly declines afterwards. Overall, there were no relevant changes observed for laboratory, ECG recordings, and vital signs following treatment with BI 409306 when compared to placebo. Only a rapid and short lasting increase in supine pulse rate of  $12.9 \pm 4.4$  bpm was detected in Chinese CYP2C19 poor metabolizers subjects treated with BI 409306 (100 mg single dose) in study 1289.4 [[c02098989-02](#)]. Following this observation, pharmacometric analysis of all available human data revealed a BI 409306 plasma concentration dependent increase in supine pulse rate reaching a maximum of 7-13 bpm (median) at high exposure end in CYP2C19 poor metabolizers treated with BI409306 at 100 mg. The maximum effects of BI 409306 on pulse rate were generally achieved at maximum BI 409306 plasma concentrations (20-30 minutes post dose) and disappeared rapidly with declining concentrations. Altogether, good to satisfactory safety and tolerability were observed in single doses of BI 409305 (up to 350mg in CYP2C19 extensive metabolizers (EM); up to 100mg in CYP2C19 poor metabolizers (PM)) in healthy young volunteers and multiple doses (14 days up to 100mg EM/50mg PM) of BI 409306 in healthy young and elderly subjects. None of the safety data presented a safety issue for further clinical trials.

Proprietary confidential information.

© 2017 Boehringer Ingelheim International GmbH or one or more of its affiliated companies. All rights reserved.  
This document may not - in full or in part - be passed on, reproduced, published or otherwise used without prior written permission.

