#### 4.1.4 Drug assignment and administration of doses for each patient

All patients who fulfil both inclusion and exclusion criteria until visit 2 will be assigned to a single blinded placebo run-in kit at the beginning of the run-in period (Visit 2).

The medication assignment will be provided through IRT. The assigned medication number must be entered in the eCRF, and the corresponding medication kit must be given to the patient. The amount of trial medication dispensed and returned will be recorded on drug accountability forms.

IRT will allocate medication kit numbers at Visit 2, 3, 5 and 6.

For blinding reasons all treatments will consist of two tablets of active drug or placebo for the morning dose and one tablet of active drug or placebo for the evening dose depending on the treatment arm. This will not be changed during the entire study.

During the run-in period patients will take 3 placebo tablets daily (2 tablets in the morning and 1 tablet in the evening) to mimic the dosing schedule during the treatment period.

Following the run-in period patients will be randomized (Visit 3) to one of the 5 treatment arms as outlined in [figure 3.1:1](#)

The first dose of the study medication will be taken at visit 2 under supervision of the investigator or site staff. At all applicable clinic visits the investigational drug will be taken during the visit under supervision of the investigator or relevant site staff. The actual visit date and time of study drug administration at the trial visit will be recorded in the eCRF.

Patients should be instructed to take the tablets orally with water at approximately the same time every day in the morning and in the evening with or without food. If a dose is missed by more than 4hrs, that dose should be skipped and the next dose should be taken as scheduled. No double doses should be taken and dose reductions are not permitted. Patients should be instructed to bring all unused drug and empty study blister / bottles to the study site.

Patients should be instructed not to take their study medication on the morning of visit days. Patients are allowed to have a light breakfast/meal before the scheduled visit. Patients who erroneously take the morning dose of study medication before coming to the clinic at visit 6 should have the visit rescheduled as soon as possible, ideally on the following day [REDACTED]

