## 6. INVESTIGATIONAL PLAN

### 6.1 VISIT SCHEDULE

All trial visits should be initiated preferentially in the morning starting before 9:00 AM. Patients should be instructed to avoid intake of the morning dose of the study medication at home at scheduled visit days as they will be dosed whilst at the study site.

All patient visits should be scheduled according to the [Flow Chart](#).

If any visit has to be rescheduled, subsequent visits should follow the original visit schedule. The trial medication packs contain sufficient medication to allow for these time windows.

The end of the trial is defined as “last patient out”, i.e. last visit completed by the last patient.

If the reason for removal of a patient from the treatment is an adverse event or an abnormal laboratory test result, the patient must be followed until complete resolution or stabilization of the event or until follow-up is agreed to be adequate by the Investigator and BI CML.

Blood samples for the optional pharmacogenomics evaluation should be collected only after obtaining separate informed consent.

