### 6.2.2 Treatment period(s)

#### Visit 3 (Randomization visit)

Visit 3 is the baseline/randomisation visit and marks the beginning of the treatment period. The neuropsychological assessments may be done on the day before the randomisation visit (last day of the screening period) if agreed between site staff and patient. In any case it needs to be ensured that the recommendations for the conduct of the neuropsychological assessments (refer to [section 6.2](#) for details) are followed.

- It is recommended to perform study procedures in the order as listed in the [Flow Chart](#).
- Study medication provided at visit 2 and returned should be collected and compliance check performed.
- Beginning with Visit 3 until end of treatment (EOT/ ED respectively) the neuropsychological assessments should always be performed approximately at the same time (in the morning) in the order as stated in the [Flow Chart](#)
- Eligible patients should be randomised using IRT. If patient does not meet inclusion/exclusion criteria at visit 3 the patient must be recorded in IRT and CRFs as a screen failure.
- Informed consent for optional pharmacogenomics sampling, if applicable should be obtained
- For diabetic patients with antidiabetic therapy: exclusion of hypoglycemia for the period of the neuropsychological assessment (documented plasma glucose concentration  $\geq 90$  mg/dl (5mmol/l) at the beginning and directly after the assessment). If glucose is too low

Proprietary confidential information.

© 2017 Boehringer Ingelheim International GmbH or one or more of its affiliated companies. All rights reserved.  
This document may not - in full or in part - be passed on, reproduced, published or otherwise used without prior written permission.

patients need to eat a snack and then be retested to confirm that the blood sugar value is above 90 mg/dl before the tests are started

- Administer the neuropsychological assessments in the following order :
  - CDR-SB
  - NTB
  - ADCS-MCI-ADL
  - ADAS-cog11
- Administration of C-SSRS (since last visit scale).
- Pre-dose vital signs (orthostatic measurements of systolic/diastolic blood pressure and pulse rate). Please see [section 5.2.5.2](#).
- [REDACTED]
- [REDACTED]
- Collection of urine and blood for safety laboratory testing.
- [REDACTED]
- [REDACTED]
- New medication kits should be dispensed and the intake of trial medication and handling of medication blisters should be discussed with the patient and the study partner.

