- The first dose of the study medication from the new kit should be taken under the supervision of the study staff.
- [REDACTED]
- Post Dose Vital Signs\_(orthostatic measurements of systolic/diastolic blood pressure and pulse rate) at 70-110 minutes should be performed. Please see [section 5.2.5.2](#).
- Patients should be advised to take the trial medication as per the drug label till the next scheduled visit. The importance of compliance to the study drug intake should be emphasized to the study partner as well. Patients should be reminded to return all used and un-used medication including the medication packaging back to the clinic at visit 5.
- Patients should be reminded not to take occasionally used sleeping aids (see [section 4.2.2.1](#)) in the evening prior to visit 5
- Patient should be reminded to NOT take any study medication on the morning of visits 4 and 5.
- Patients are allowed to have a light breakfast/ meal before coming to the study site.
- Patient should be reminded to inform the study site in case of adverse events.

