7.8.1 Adverse events

7.8.1.1 Assignment of AEs to treatment

Unless otherwise specified, the analyses of adverse events will be descriptive in nature. All analyses of AEs will be based on the number of patients with AEs and NOT on the number of AEs.

For analysis multiple AE occurrence data on the CRF will be collapsed into an AE event provided that all of the following applies:

All AE attributes are identical (LLT, intensity, action taken, therapy required, seriousness, reason for seriousness, relationship, outcome).

The occurrences were time-overlapping or time-adjacent (time-adjacency of 2 occurrences is given if the second occurrence started on the same day or on the day after the end of the first occurrence)

For further details on summarization of AE data, please refer to [\(2, 3\)](#)

The analysis of adverse events will be based on the concept of treatment emergent adverse events. That means that all adverse events occurring between first drug intake till last drug intake + residual effect period will be assigned to the randomized treatment. All adverse events occurring before first drug intake will be assigned to 'screening' and all adverse events occurring after the residual effect period will be assigned to 'post-treatment' (for listings only). For details on the treatment definition, see [section 6.1](#).

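### The 12:00 default for a missing first-dose time in SAP Table 6.1:2 is not conservative: a brief event after a pre-noon first dose could drop out of the treatment-emergent tables

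*SAP*

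**What the plan says.** SAP 6.1, Table 6.1:2, sets the start of the treatment period by date and clock time. The entry for the clock time is "Time of first administration of study medication 12:00 if missing". The run-in row has the same default. The text under the table starts the on-treatment period at the first intake of randomised drug, but ends the run-in by date only.

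SAP 7.8.1.1 counts AEs from first drug intake to the end of the residual effect period under the randomised treatment. For earlier ones it says "All adverse events occurring before first drug intake will be assigned to" screening, although Table 6.1:2 has a separate run-in period between screening and treatment.

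On the timing of the first dose, the protocol says:

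- Section 6.1: "All trial visits should be initiated preferentially in the morning starting before 9:00 AM".
- Section 6.2.2, Visit 3: "The first dose of the study medication from the new kit should be taken under the supervision of the study staff".
- The same section lists the tests ahead of that dose ("Administer the neuropsychological assessments in the following order") but also allows them earlier: "The neuropsychological assessments may be done on the day before the randomisation visit".
- Section 4.1.4: "The actual visit date and time of study drug administration at the trial visit will be recorded in the eCRF".

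On the timing of drug effects, the clinical safety text in section 1.2 says that visual side effects were the most frequent drug-related events in healthy volunteers, and that they "occurred shortly after dosing and mostly resolved within 1 h".

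**The concern.** A default for a missing dose time should not work against finding the effects the drug is already known to have. Noon is late for a dose given at a visit that preferably begins before 9:00, above all when the test battery was done the day before. If the fallback is used after a true morning dose, the hour in which visual effects are expected can lie before the imputed start of treatment. An event that begins and ends in that hour would be classed as pre-treatment.

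Protocol 7.3.3 keeps as treatment-emergent an AE that starts before first intake and worsens under treatment. That does not recover an event that has already resolved. What is at stake is the completeness of the treatment-emergent AE tables for first-dose effects.

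**Working it through.** There is no computed figure in the plan to reproduce; 12:00 is a rule. The check is one of clock times.

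**Inputs**
- Imputed start of treatment when the time is missing: 12:00 (SAP Table 6.1:2).
- Period of interest: the first 60 minutes after the dose, because visual effects mostly resolve within 1 h (Protocol 1.2).
- Illustrative onset delays: 20 and 30 minutes. This is when Protocol 1.2 places the maximum pulse effect; it gives no minute value for the onset of visual effects.
- True dose time D: not stated in either document, so assumed over a range.

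**Formulas**
- Minutes of the first post-dose hour that fall before the imputed start = max(0, min(60, 12:00 − D)).
- An event with a known onset time is misplaced if D + delay is earlier than 12:00.
- Pre-dose minutes wrongly counted as on treatment = max(0, D − 12:00).

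**Results**

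| Assumed D | First-hour minutes before 12:00 | Event at +20 min misplaced | Event at +30 min misplaced | Pre-dose minutes counted as on treatment |
|---|---|---|---|---|
| 08:00 to 11:00 | 60 | yes | yes | 0 |
| 11:30 | 30 | yes (11:50) | no (12:00) | 0 |
| 11:45 | 15 | no (12:05) | no (12:15) | 0 |
| 12:00 | 0 | no | no | 0 |
| 12:30 | 0 | no | no | 30 |

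The cut-offs are 12:00 − 20 min = 11:40 and 12:00 − 30 min = 11:30. As an example, take D = 10:00 with the time missing, and an event from 10:25 to 11:00. It lies wholly before 12:00, so it is not treatment-emergent and the worsening clause does not apply.

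**Conditions.** The misplacement needs three things together: the dose time is missing, the AE has an onset clock time, and that onset is before 12:00. If the dose time is recorded, no minutes are affected.

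**If only an onset date is held.** Protocol 5.2.2.2 asks the investigator for the date of onset and mentions no time. The text under Table 6.1:2 runs the run-in up to the date of the first randomised dose and starts treatment at first intake on that same date, so a date alone does not separate the two. SAP 6.6.3, whose heading covers AE dates and times, refers to a sponsor standard that is not among the documents. The result in this case cannot be derived.

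**The case against.** The strongest reply is that the fallback should hardly ever be used. The dose is supervised, its time must be entered in the eCRF, and every Visit 3 patient has pulse readings timed from it (Protocol 5.2.5.2). This stands, and it is why the point is small. It does not make the default a good one: the SAP provides for a missing time, so the provision should be safe.

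Three stronger readings are tempting, and the documents do not support them.

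- **That early events would be classed as run-in as a matter of course.** Onset clock times are not shown to be collected. The before-9:00 start is a preference and refers to the visit, not the dose. When the full battery is done that day, the dose follows four cognitive and functional assessments, the C-SSRS, vital signs and laboratory samples of unstated duration, and may be near noon or later. It follows that the error need not always be towards fewer drug effects.
- **That patients removed at Visit 3 under the pulse rule could vanish from the counts.** That rule (Protocol 3.3.4.1) works on readings timed from the dose, out to 90±20 minutes. Staff need the dose time to apply it, so these patients are the least likely to have it missing.
- **That pulse readings are moved by the 12:00 rule.** A vital-sign change becomes an AE only if the investigator considers it clinically relevant (Protocol 5.2.2.1), and SAP 6.7 places safety measurements by day, not by clock time.

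**Conclusion.** The point holds as a low-impact improvement. The 12:00 default is not conservative for a first dose that may be given before noon. Where the dose time is missing and an onset time is held, a brief event soon after such a dose could be left out of the treatment-emergent tables. For any assumed dose time from 08:00 to 11:00 the whole first hour is exposed; for a dose after noon the error reverses.

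The size cannot be quantified from the documents, which give neither the share of missing dose times nor the rate of events confined to the first dose. A reader might assume, say, 2% to 10% and 10% to 20%. That gives 48 × 0.02 × 0.10 = 0.1 to 48 × 0.10 × 0.20 = 0.96 patients per active arm of 48. These rates are assumptions, and the product also takes every dose as before noon and every onset time as available, so for those rates it is a ceiling and not an estimate. It shows only that the issue is minor even on generous inputs. Events that recur after later doses are counted in any case.

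The labels should also be made consistent: by Table 6.1:2 such an event falls in the run-in, by SAP 7.8.1.1 in screening. Under either label it is not treatment-emergent.

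**What to change.** In the treatment row of Table 6.1:2, replace the 12:00 default with this rule: when the dose time or the AE onset time is missing, any AE with onset on the date of the first randomised dose is assigned to randomised treatment, unless it is documented as starting before the dose. This covers both the missing dose time and the case where only an onset date is held.

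Align the text under the table and SAP 7.8.1.1 with this rule, so that the run-in and treatment periods do not both claim the first-dose date and one label is used for AEs between the first run-in dose and the first randomised dose. The same default in the run-in row separates only screening from run-in, so it does not affect the treatment-emergent tables.

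The cost is one SAP line, matching edits to the text and one programming rule. The downside is that an occasional complaint that in fact began before the dose on Day 1 is counted as treatment-emergent. That would happen in all arms alike. No dose, visit procedure or withdrawal rule changes.
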